#### **9.3.2.5 *Change in breathlessness and cough scores***

Change in breathlessness and cough scores over the treatment period will be analysed using the same methods described for total BCSS score in [Section 9.3.2.4](#).

Absolute values and the change from baseline in breathlessness, cough and sputum score will be summarised over the entire study period. The change from baseline in each symptom score will also be summarised in shift tables.

#### **9.3.3 NEWS2 Score**

The absolute NEWS2 scores and the change from baseline in NEWS2 score will be summarised for hospitalised patients at each scheduled assessment. Generally, NEWS2 score will only be calculated from the data recorded in the NEWS2 CRF. However, baseline NEWS2 score will be calculated from the data entered in the vital signs and level of confusion CRFs for the last assessment prior to first dose. NEWS2 scores will be calculated and summarised from data collected in the NEWS2 CRF for the Pre-dose and Day 1 assessments, however the change from baseline will not be summarised because as per the protocol these assessments could be pre or post dose.

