6.9 NEWS2

The data required for NEWS2 will be collected by the site staff and NEWS2 will be calculated by the Sponsor.

NEWS2 is a tool developed by the Royal College of Physicians, which improves the detection and response to clinical deterioration in adult patients and is a key element of patient safety and improving patient outcomes (12).

NEWS2 is based on a simple aggregate scoring system in which a score is allocated to physiological measurements, already recorded in routine practice, when patients present to, or are being monitored in hospital.

Six simple physiological parameters form the basis of the scoring system:

1. Respiration rate
2. Oxygen saturation
3. Any supplementary oxygen
4. Temperature
5. Systolic blood pressure
6. Heart rate
7. Alert, Voice, Pain, Unresponsive.

The highest NEWS2 score for each calendar day should be collected. The highest NEWS2 score will be recorded daily, for each calendar day, whilst the patient is hospitalised. When the patient is discharged home, NEWS2 will not be recorded.

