#### 5.3.2 *Derivation of NEWS2 Scores*

The NEWS2 score will be calculated using the following six parameters:

1. respiration rate
2. oxygen saturation
3. systolic blood pressure
4. pulse rate
5. level of consciousness or new confusion
6. temperature.

Each parameter will be assigned a score between 0 and 3 according to the chart in [Appendix I](#) and the NEWS2 score is calculated as the sum of the individual parameter scores, providing that all respective scores are non-missing. If any individual parameter scores are missing the NEWS2 score will also be missing.

For the pre-treatment/pre-baseline assessment, the NEWS2 score will be derived using data from scheduled vital signs page of the eCRF. For any post-baseline assessments, the NEWS2 score will be derived using data from the scheduled NEWS2 page.

NEWS2 score will also be categorised as per table 1.

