## **10.2 Vital Signs**

Systolic blood pressure, diastolic blood pressure, heart rate, body temperature, respiratory rate and oxygen saturation absolute and change from baseline values will be summarised by descriptive statistics for each study day. The number and percentage of patients receiving oxygen at each assessment will also be presented. Vital signs will not be collected following discharge from hospital.

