## **10.3 Level of Consciousness or new Confusion**

Level of consciousness or new confusion will be summarised by shift tables from baseline to each post baseline timepoint. Data will be collected whilst patients are hospitalised only.

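### NEWS2 change from baseline subtracts one pre-dose reading from later daily maxima, which shifts the mean within-arm change toward worsening

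*SAP*

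**What the plan says.** Changes in NEWS2 while in hospital are a named secondary endpoint (Protocol 2.4, SAP 4.2.3). Two sources feed the change score.

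- **Baseline.** SAP 5.3.2: "For the pre-treatment/pre-baseline assessment, the NEWS2 score will be derived using data from scheduled vital signs page of the eCRF". SAP 9.3.3 adds the consciousness form and fixes the time point: "baseline NEWS2 score will be calculated from the data entered in the vital signs and level of confusion CRFs for the last assessment". The assessment meant is the one that precedes dosing. Under Protocol 6.8 and footnote 4 of the study schedule, vital signs are one daily assessment, done with the physical examination at a roughly constant time of day.
- **Post-baseline.** SAP 5.3.2: "For any post-baseline assessments, the NEWS2 score will be derived using data from the scheduled NEWS2 page". Protocol 6.9 defines what that page contains: "The highest NEWS2 score will be recorded daily, for each calendar day, whilst the patient is hospitalised".

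SAP 9.3.3 summarises absolute scores and change from baseline for hospitalised patients at each scheduled assessment. It omits the change for Pre-dose and Day 1, because the NEWS2 page for those days may include post-dose values. It does not mention that the two sources record different kinds of value.

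**The concern.** A maximum of several readings and a single reading are different quantities. If the scheduled reading is one of the day's readings, that day's maximum cannot lie below it, and it lies above it whenever another reading is worse. A patient whose underlying condition is constant will therefore, on average, show a rise from a single-reading baseline to a daily-maximum follow-up. In a patient who is improving, the same mechanism hides part of the improvement.

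At stake is the level of the within-arm change, which is the quantity that the endpoint names. A reader of the table could see deterioration, or slow improvement, that comes only from the choice of data page.

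**Working it through.** The documents give no NEWS2 variance, number of daily readings or expected change, so there is no planned figure to reproduce. The direction follows from the text. The size needs assumptions.

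**Inputs from the documents.** Baseline is one reading (SAP 5.3.2, 9.3.3). Follow-up is the daily maximum (Protocol 6.9). Change is reported from Day 2 on (SAP 9.3.3). There are 305 patients per arm (SAP section 6).

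**Assumptions, not in the documents.** Patients are stable; true scores have mean 5 and between-patient SD 1.5; readings vary independently and normally around the patient's level, with within-day SD 0.5, 1.0 or 1.5 points; there are 1, 2, 4 or 6 readings a day; scores are rounded to integers.

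**Formula.** Expected false change = E[maximum of k readings] − E[one reading] = SD × m(k), where m(k) is the expected maximum of k standard normal values: m(1) = 0, m(2) = 0.564, m(4) = 1.029, m(6) = 1.267.

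| Readings per day | SD 0.5 | SD 1.0 | SD 1.5 |
|---|---|---|---|
| 1 | 0 | 0 | 0 |
| 2 | 0.5 × 0.564 = +0.28 | +0.56 | 1.5 × 0.564 = +0.85 |
| 4 | 0.5 × 1.029 = +0.51 | +1.03 | 1.5 × 1.029 = +1.54 |
| 6 | 0.5 × 1.267 = +0.63 | +1.27 | 1.5 × 1.267 = +1.90 |

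A simulation of 400,000 stable patients per cell, with rounded scores, agreed with every cell to within 0.01.

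**Individual patients.** At SD 1 with 4 readings a day, 66% of stable patients show a rise, 11% a fall, and the remaining 23% no change.

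**Matched sources.** With a daily maximum on both sides, the mean change is 0.00 in every setting, and at SD 1 with 4 readings 31% rise and 31% fall. A single reading on both sides also gives 0.00.

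**Between arms.** In 2,000 simulated trials with 305 stable patients per arm (SD 1, 4 readings), the mean between-arm difference in change was 0.005 points, in effect zero.

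**The case against.** The other side has several fair points.

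- **The choice was deliberate.** Day 0 may also be the first dosing day, so a Day 0 daily maximum can be post-dose. Using a pre-dose reading avoids that, and the SAP gives the reason. This stands as a reason for the baseline source. It does not justify a different kind of value at follow-up.
- **A same-source series is already planned.** SAP 9.3.3 also summarises NEWS2-page scores for Pre-dose and Day 1, so absolute daily maxima run from Pre-dose onward. That helps an attentive reader, but it leaves the change score uncorrected.
- **The size is unknown and may be zero.** No minimum observation frequency is stated, and Protocol 5.3.4 lets sites reuse components already measured that day. This stands: the table above is a range under assumptions.
- **Nothing inferential depends on it.** NEWS2 is summarised without a model or test, is absent from SAP Table 7, and lies outside the multiple testing strategy. This stands.
- **Matching data may be incomplete.** Protocol 6.8 does not list oxygen saturation among vital signs, but SAP 10.2 does: "respiratory rate and oxygen saturation absolute and change from baseline values will be summarised by descriptive statistics for each study day". For consciousness, SAP 10.3 promises data "summarised by shift tables from baseline to each post baseline timepoint" without saying whether they come from their own scheduled form or from the NEWS2 page. This stands, and the fix must check it.

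A reader might also infer that the NEWS2 clinical risk categories in SAP 5.3.2 will falsely migrate upward from baseline. The documents do not support making that a finding: 9.3.3 specifies no table of baseline against later categories, and the size of any migration would depend strongly on the assumed true score.

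**Conclusion.** The mismatch is in the current text of both documents, and its direction follows whenever more than one set of observations is taken in a day. The planned mean within-arm change is then biased toward worsening from Day 2 on, by about +0.3 to +1.9 points under the assumed SDs and 2 to 6 readings a day, and by 0 with one reading.

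Two stronger readings go too far. A reader might infer that every stable patient will appear to worsen, but the shift is an average: at SD 1 with 4 readings, about a third of stable patients show no rise. A reader might also infer that the comparison of SNG001 with placebo is distorted. The shift is about the same in both arms unless observation frequency or within-day variability differs by arm, and nothing in the documents indicates that. The primary and key secondary conclusions are unaffected. This is a correctable flaw in one descriptive secondary endpoint and should be put right before the table is produced.

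**What to change.** Amend SAP 5.3.2 and 9.3.3 as follows.

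1. Confirm from the CRF that level of consciousness is recorded post-baseline at the scheduled assessment, and not only on the NEWS2 page. Confirm also that the vital-signs page carries the other NEWS2 components at those visits.
2. If so, derive NEWS2 change from baseline up to Day 15 from the scheduled daily vital-signs and level-of-consciousness data, the same source as baseline.
3. Keep the daily-maximum NEWS2 as absolute values from Pre-dose to Day 28, so that the later in-hospital data and the measure set by the protocol are still reported.
4. If a change based on daily maxima is still shown, for example after Day 15, take its baseline from Day 0 daily-maximum records confirmed as pre-dose. Otherwise label it in the table as a daily maximum minus a single reading. The same label applies throughout if step 1 fails.

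The cost is SAP wording and one more derivation; if step 1 is confirmed, no new data are needed. The downside is that no same-source change exists after Day 15, because scheduled vital signs end there.

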#### **9.3.4 Quality of Life**

Quality of life as measured by the EQ-5D-5L will be summarised by descriptive statistics of the crosswalk index value, the LSS, the Visual Analogue Scale (VAS) and the usual activities dimension at each scheduled visit.

#### **9.3.5 General Anxiety**

GAD-7 total scores will be summarised by descriptive statistics and the number and percentage of patients within each anxiety severity category will be displayed at each scheduled assessment.

#### **9.3.6 Depression**

PHQ-9 total scores will be summarised by descriptive statistics and the number and percentage of patients within each depression severity category will be displayed at each scheduled assessment.

#### **9.3.7 Fatigue**

FACIT-FS total scores will be summarised by descriptive statistics at each scheduled assessment.

#### **9.3.8 Pain**

Descriptive statistics will be presented at each post baseline visit for each pain severity score category, the overall pain severity score and the pain interference score.

### 9.3.9 COVID-19 Symptom Assessments

The number and percentage of patients with any symptom, each individual symptom and any other symptoms associated with COVID-19 will be presented both overall and at each scheduled time point.

## 10 Safety Analyses

All outputs for safety outcomes will use the Safety analysis population.

### 10.1 Adverse Events

Adverse events will be recorded from the time informed consent is given 28 days after the last administration of the study medication. All AEs will be coded using the latest available version of the MedDRA and will be categorized by intensity (mild/moderate/severe) and relationship (unrelated/unlikely to be related/possibly related/probably related/definitely related).

A treatment-emergent adverse event (TEAE) is defined as any event not present prior to the administration of study drug or any unresolved event already present before administration of study drug that worsens in intensity following exposure to the treatment. Where dates are missing or partially missing, AEs will be assumed to be treatment-emergent unless they clearly started prior to treatment (as indicated by the month/year if the day is missing etc.).

Summary tables will contain the cumulative incidence rate and the number of events where applicable. A subject who has multiple events in the same SOC and PT will be counted only once in the subject counts but all events will be included. Adverse event summaries will be ordered by the international SOC order ([Appendix III](#)) and decreasing frequency of PT within SOC, in the active arm overall column.

Summaries of TEAEs by SOC and PT will include the following:

- Incidence of TEAEs
- Incidence of serious TEAEs
- Incidence of serious related TEAEs
- Incidence of TEAEs by relationship
- Incidence of TEAEs by severity
- Incidence of TEAEs leading to discontinuation
- Incidence of TEAEs leading to death
- Incidence of related TEAEs leading to death.
- Incidence of TEAEs of special interest.
- 

An adverse event summary will summarise the number of TEAEs in each of the above categories alongside 95% Newcombe confidence intervals for the differences in proportions between treatment arms.

Summaries of TEAEs by PT will include the following:

- Incidence of TEAEs
- Incidence of serious TEAEs

- Common TEAEs (occurring in at least 5% of the total study population).

The summary of common TEAE will include 95% Newcombe confidence intervals for the differences in proportions between treatment arms.

In summaries including relationship to study treatment, the following relationships will be considered related: 'Definitely related', 'Probably Related', 'Possibly Related'. 'Unlikely to be Related' and 'Not related' will be considered unrelated.

In summaries including intensity, the following intensity categories will be summarized: 'Mild', 'Moderate', 'Severe'. Subjects will be counted once under each severity category if the same event was observed at different severities.

An adverse event of special interest (AESI) is an AE that meets the following criteria:

- Moderate or worse palpitations during the dosing period and up to 24 hours after last dose.
- Severe bronchospasm with 4 hours of investigational agent/placebo administration (symptoms causing inability to perform usual social and functional activities and deemed related to the study product as determined by the site investigator).

Adverse events which are coded to more than one preferred term will be counted once under each term.

A listing of serious AEs will also be produced.

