**5.2 Randomisation and Blinding**

This is a double-blind study. Patients will be randomised to one of two treatment groups (SNG001 or placebo) in a 1:1 randomisation ratio. Randomisation is stratified by study site.

- Arm 1: 305 patients - SNG001 - contents of 2 syringes\* per dose.
- Arm 2: 305 patients - Placebo - contents of 2 syringes† per dose.

\* Each syringe contains CCI mL of SNG001 nebuliser solution containing CCI MIU/mL interferon- $\beta$ 1a.

† Each syringe contains CCI mL of formulation buffer.

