## 6 Sample Size

A sample size of 610 subjects in total using a 1:1 randomisation ratio (305 subjects per treatment arm) has been chosen to provide at least 90% power to detect a hazard ratio of 1.45 in time to hospital discharge and a hazard ratio of 1.7 in time to recovery and at least 95% power to declare statistical significance on at least one of the primary endpoints. This sample size has been calculated using a global 2-sided alpha level of 0.05 and adjusting for the Hochberg procedure to allow for multiple comparisons. This sample size also allows for an interim analysis to assess futility after the first 300 randomised subjects (150 subjects per treatment arm) have completed the Day 35 assessment or have withdrawn from the study. The futility analysis is planned to be non-binding.

The power of the study was confirmed via simulation as follows:

Time to recovery and time to discharge in the placebo subjects were drawn from exponential distributions with rate parameters:

$$\text{Placebo Time to Sustained Recovery} \sim \text{Exp}\left(\frac{\log\left(\frac{100}{70}\right)}{28}\right) \text{ and}$$

$$\text{Placebo Time to Sustained Discharge} \sim \text{Exp}\left(\frac{\log\left(\frac{100}{30}\right)}{28}\right)$$

In the simulations, this gives the placebo arm:

- a median time to recovery (50% recovery) of approximately 54.4 days and a 30% recovery at exactly 28 days

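### The common-TEAE table selects preferred terms at 5% of both arms pooled, so a term in 5% to just under 10% of SNG001 patients and few or no placebo patients can miss the only planned by-term between-arm interval

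*SAP*

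**What the plan says.** SAP 10.1 (Adverse Events) plans three kinds of TEAE summary that matter here.

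- Unfiltered incidence tables, by SOC and PT and again by PT alone. The SOC/PT set is repeated for serious events, by relationship, by severity, and for events leading to discontinuation or death. No intervals are specified for these tables.
- An overview table: "An adverse event summary will summarise the number of TEAEs in each of the above categories alongside 95% Newcombe confidence intervals". On its ordinary reading this gives one row per category (any TEAE, serious, related, special interest and so on), not one per preferred term.
- A by-PT table limited to common events, selected by "Common TEAEs (occurring in at least 5% of the total study population". For this table, "The summary of common TEAE will include 95% Newcombe confidence intervals for the differences in proportions between treatment arms".

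On the population, SAP 10 states: "All outputs for safety outcomes will use the Safety analysis population". SAP 7.1.3 defines that population as dosed patients, grouped by treatment received, with anyone who ever received SNG001 counted as SNG001. Its size is not given. Neither SAP 10.1 nor protocol 8.6 sets a threshold within an arm.

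**The concern.** A pooled threshold asks how often an event occurs in the whole trial. A table of between-arm differences is there to show where the arms differ. With equal arms, an event confined to one arm has a pooled rate of half its rate in that arm, so it must reach about 10% there before the pooled rate reaches 5%. An event equally frequent in both arms needs only about 5% in each.

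The filter therefore favours balanced terms over asymmetric ones. Balanced terms are likely to be plentiful in this trial: protocol 7.1 requires new COVID-19 symptoms that start after treatment begins to be reported as AEs, and worsening symptoms too if they are clinically significant or lead to treatment. A non-serious tolerability effect of an inhaled product is the kind of term that could sit at 5% to 10% on SNG001 and near zero on placebo. At stake is whether the table that carries by-term uncertainty shows such a term.

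**Working it through.** The documents state no calculated figure for this rule, so there is none to reproduce. The check applies the rule to the planned sample size.

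**Inputs**
- Total and allocation: "A sample size of 610 subjects in total using a 1:1 randomisation ratio (305 subjects per treatment arm" (SAP 6); "Arm 1: 305 patients - SNG001" and "Arm 2: 305 patients - Placebo" (SAP 5.2). 305 + 305 = 610.
- Threshold: 5% of the arms together (SAP 10.1).
- Assumption: 305 per arm in the Safety population. It is varied in step 4.

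**Step 1: the cut.** 0.05 × 610 = 30.5, so a term needs 31 patients. A total of 30 gives 30/610 = 4.92% and is omitted. A total of 31 gives 31/610 = 5.08% and is kept.

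**Step 2: the Newcombe interval.** The Wilson limits for each arm, with z = 1.96, are

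(l, u) = [p + z²/(2n) ± z√(p(1−p)/n + z²/(4n²))] / (1 + z²/n).

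Then, with d = p₁ − p₂,

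- lower limit = d − √[(p₁−l₁)² + (u₂−p₂)²]
- upper limit = d + √[(u₁−p₁)² + (p₂−l₂)²]

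For 30 v 0, in percentage points: p₁ = 9.836 with Wilson limits 6.977 and 13.694; p₂ = 0 with limits 0 and 1.244.

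- Lower: 9.836 − √(2.859² + 1.244²) = 9.836 − 3.118 = 6.72
- Upper: 9.836 + √(3.858² + 0²) = 13.69

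**Step 3: which terms are shown.**

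| SNG001 v placebo (of 305 each) | Rates | Pooled | In table? | Difference (95% CI), points |
|---|---|---|---|---|
| 30 v 0 | 9.84% v 0% | 4.92% | No | 9.84 (6.72 to 13.69) |
| 25 v 5 | 8.20% v 1.64% | 4.92% | No | 6.56 (3.20 to 10.30) |
| 22 v 8 | 7.21% v 2.62% | 4.92% | No | 4.59 (1.15 to 8.29) |
| 20 v 10 | 6.56% v 3.28% | 4.92% | No | 3.28 (−0.21 to 6.95) |
| 18 v 12 | 5.90% v 3.93% | 4.92% | No | 1.97 (−1.57 to 5.61) |
| 16 v 15 | 5.25% v 4.92% | 5.08% | Yes | 0.33 (−3.30 to 3.98) |
| 31 v 0 | 10.16% v 0% | 5.08% | Yes | 10.16 (7.00 to 14.07) |

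**Step 4: other Safety population sizes.** The largest SNG001-only count that is omitted is the pooled cut minus one.

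| SNG001/placebo | Largest omitted count | SNG001 rate |
|---|---|---|
| 280/280 | 27 | 9.64% |
| 300/300 | 29 | 9.67% |
| 305/290 | 29 | 9.51% |
| 290/305 | 29 | 10.00% |
| 310/310 | 30 | 9.68% |
| 320/290 | 30 | 9.38% |
| 290/320 | 30 | 10.34% |

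Across these assumed sizes the largest omitted one-arm rate is about 9.4% to 10.3%, so the result does not hinge on exactly 305 per arm. Reading the total study population as ITT rather than Safety also pools the arms and leads to the same place.

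**Step 5: a threshold in either arm.** 0.05 × 305 = 15.25, so the cut is 16 of 305 (5.25%) in one arm. The first five rows of the step 3 table would then be shown. No row now shown would be lost, because a pooled rate of at least 5% requires at least one arm to be at 5% or more.

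**The case against.** The strongest reply is that nothing is withheld. A 30 v 0 term appears with its count in each arm in the unfiltered SOC/PT and PT tables, and SAP 10.1 sorts preferred terms by frequency in the active arm, so it would rank high within its SOC. Anyone can compute the Newcombe interval from the counts and denominators. That stands.

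Second, protocol 8.6 plans AE reporting as descriptive and asks for no between-arm intervals. No test, decision rule or estimate depends on the filter. That also stands, and it limits the point to presentation.

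Third, the overview table gives intervals at any frequency for serious, related, severe, treatment-ending, fatal and special-interest events. This stands for those categories as aggregates. It does not cover an individual non-serious term: the special-interest list in SAP 10.1 holds only moderate or worse palpitations and severe related bronchospasm within 4 hours of dosing.

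Fourth, the affected band is limited. At 305 per arm any term in 31 or more SNG001 patients is always kept, and terms below 5% in both arms are left out under either rule. Some omitted terms are also uninformative: the intervals for 20 v 10 and 18 v 12 include zero.

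A reader might infer that the rule hides drug reactions, or drops every event that is frequent on SNG001 and rare on placebo. The documents do not support either reading, for the first and fourth reasons above.

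**Conclusion.** The point holds as a minor reporting weakness. The pooled rule can exclude a preferred term seen in 5% to just under 10% of SNG001 patients and in few or no placebo patients from the only planned by-term table with between-arm intervals, while keeping a balanced term of similar total frequency. The omitted differences can be as large as 9.8 points (95% CI 6.7 to 13.7) at an assumed 305 per arm. The loss is the pre-specified by-term difference and interval; the counts by arm remain. The conclusion rests on reading the total study population as both arms together, on the overview table having one row per category, and on a Safety population near the planned size with roughly equal arms.

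**What to change.** In SAP 10.1, change the definition to: *Common TEAEs (occurring in at least 5% of patients in either treatment arm of the Safety population)*, and keep the 95% Newcombe intervals. This also names the denominator explicitly. The cost is one line of SAP text, one table filter and a few more rows. It needs no new data and has no effect on efficacy testing or alpha.

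It may be tempting also to admit any term with an observed difference of at least 2 percentage points. That should not be added, because it selects rows on the quantity being estimated. At 305 per arm, 2 points is 6.1 patients, so a gap of 7 qualifies. With a true rate of 5% in both arms, chance alone produces a gap that large about 23% of the time (about 12% at a true rate of 3%), which would fill the table with noise.

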7.4.1.1 Causality

Causality is the relationship between the study medication and the occurrence of the AE. Determination of causality is based on the Investigator's clinical judgment regarding the likelihood that the study medication caused the AE and may include consideration of some or all of the following factors:

- Alternative possible causes of the AE, including the patient's underlying disease or co-morbid conditions, other drugs, other host and environmental factors.
- The temporal sequence between the study medication exposure and the AE.
- Whether the clinical or laboratory manifestations of the AE are consistent with known actions or toxicity of the study medication.

Investigators need to assess the relationship of AEs to the study medication by consulting the IB and using the following definitions:

Definitely related: A causal relationship of the onset of the event relative to administration of the study medication and there is no other cause to explain the event.

Probably related: A causal relationship is clinically/biologically reasonable relative to the administration of the study medication and the event is more likely explained by exposure to the study medication than by other factors or causes.

Possibly related: A causal relationship is clinically/biologically reasonable relative to the administration of the study medication, but the event could have been due to another equally likely cause.

Unlikely to be related: A causal relationship is considered unlikely to be related to use of the study medication if there are factors (evidence) explaining the occurrence of the event (e.g., progression of the underlying disease, concomitant medication more likely associated with the event) or a convincing alternative explanation for the event.

Unrelated: A causal relationship is not reasonably related in time to the administration of the study medication, or exposure to the study medication has not occurred.

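### The bronchospasm AESI counts only severe events that the site judges drug-related, so other bronchospasm below the 5% common-TEAE threshold gets by-arm counts but no between-arm interval

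*SAP*

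**What the plan says.** SAP 10.1 (Adverse Events) defines two AESIs with different filters.

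- Palpitations: "Moderate or worse palpitations during the dosing period and up to 24 hours after last dose". There is no causality condition.
- Bronchospasm: "Severe bronchospasm with 4 hours of investigational agent/placebo administration" (presumably meaning within 4 hours), with the added condition that the event is "deemed related to the study product as determined by the site investigator".

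The same section plans TEAE tables by system organ class and preferred term. They include "Incidence of TEAEs of special interest", "Incidence of TEAEs by severity" and "Incidence of TEAEs by relationship", as well as all TEAEs and serious TEAEs. SAP 8 gives every summary table a column per arm.

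Between-arm intervals are planned in two places. The first is by category: "An adverse event summary will summarise the number of TEAEs in each of the above categories alongside 95% Newcombe confidence intervals". The second is by preferred term, but only for terms that occur in at least 5% of the total study population.

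Protocol 7.4.1.1 defines the causality scale. For the grade of unlikely, it illustrates the explaining factors with "e.g., progression of the underlying disease, concomitant medication more likely associated with the event". An event with another equally likely cause is graded possibly related, and SAP 10.1 analyses that grade as related.

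**The concern.** SNG001 is nebulised, and bronchospasm is the local airway event that the SAP itself singles out. Yet it has the stricter of the two AESI filters, on both severity and attribution, and the documents give no reason for the difference.

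The trial is randomised and double-blind, so background bronchospasm is expected equally in both arms and the placebo arm already accounts for it. A site judgement of relatedness is not needed for that comparison, and it can discard events that the drug did cause. Every patient enters with COVID-19 that requires oxygen, so a competing explanation is always at hand.

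At stake is how an imbalance in moderate bronchospasm, or in bronchospasm judged not related, would be reported. If the term stays below 5%, the reader would have counts by arm and no estimate of the difference with its uncertainty.

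**Working it through.** The documents state no bronchospasm rate, AESI rate or safety power, so there is no figure of the plan to reproduce. The check traces where each kind of event goes, then illustrates the size.

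**Where events go (SAP 10.1)**

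| Bronchospasm event | In AESI count and interval | In by-arm preferred-term, severity and relationship tables | Own interval |
|---|---|---|---|
| Severe, in the 4-hour window, judged related | Yes, pooled with palpitations | Yes | Only if the term reaches 5% |
| Severe, judged unlikely or unrelated | No | Yes | Only if the term reaches 5% |
| Moderate or mild, any attribution | No | Yes | Only if the term reaches 5% |

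**Threshold.** Taking the safety population as the planned 610 (Protocol 8.1), 0.05 × 610 = 30.5, so a term needs 31 patients.

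**Illustration 1: assumed counts, 305 per arm.** For each arm with proportion p, take the Wilson 95% limits (l, u). The Newcombe limits for d = p1 − p2 are

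- lower: d − √[(p1 − l1)² + (u2 − p2)²]
- upper: d + √[(u1 − p1)² + (p2 − l2)²]

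For 15/305 v 3/305:

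- p1 = 4.92% (Wilson 3.00 to 7.96) and p2 = 0.98% (0.34 to 2.85), so d = 3.93 points
- lower = 3.93 − √(1.915² + 1.868²) = 3.93 − 2.68 = 1.26
- upper = 3.93 + √(3.037² + 0.649²) = 3.93 + 3.11 = 7.04

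| Assumed SNG001 v placebo | Difference, points (95% CI) | Pooled rate | By-term interval planned? |
|---|---|---|---|
| 15 v 3 | 3.9 (1.3 to 7.0) | 18/610 = 2.95% | No |
| 12 v 2 | 3.3 (0.9 to 6.1) | 14/610 = 2.3% | No |
| 27 v 3 | 7.9 (4.6 to 11.6) | 30/610 = 4.92% | No |

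Fisher p for 15 v 3 is 0.007. If none of these events were both severe and judged related, bronchospasm would add 0 v 0 to the AESI row.

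**Illustration 2: a partial filter.** With 12 v 3 in all, the difference is 2.95 points (0.45 to 5.84). If only 2 v 0 pass the AESI filter, it is 0.66 points (−0.68 to 2.36).

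**Illustration 3: assumed true rates of 4% v 1%.** The chance that a two-sided 5% comparison detects the difference, with n = 305 per arm and p̄ the mean of p1 and p2, is

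Φ{[d − 1.96√(2p̄(1 − p̄)/n)] / √[(p1(1 − p1) + p2(1 − p2))/n]}

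- All bronchospasm: (0.03 − 1.96 × 0.01264)/0.01258 = 0.41, which gives 66%.
- If 30% of events pass in each arm (1.2% v 0.3%): (0.009 − 1.96 × 0.00699)/0.00698 = −0.67, which gives 25%.
- If 50%, 20% or 10% pass: 39%, 18% and 11%.

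The normal approximation is rough at the lowest rates, and the SAP plans no formal safety test. These figures show only how information falls as events are filtered out.

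**The case against.** The other side has a strong case, and much of it stands.

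- **Nothing is hidden.** A reader might infer that the AESI row is the only between-arm comparison planned for bronchospasm. It is not. All treatment-emergent bronchospasm is tabulated by arm by preferred term, severity and relationship, and the term gets its own Newcombe interval if it reaches 5%. Protocol 7.1 also requires new COVID-19 symptoms after the start of treatment to be reported as AEs, so capture does not depend on the AESI definition. Below 5% the missing item is the interval, which a reader could calculate from the counts.
- **Bronchospasm that might be due to COVID-19 is not automatically lost.** A reader might infer that any such event drops out. The documents do not support that: with COVID-19 as an equally likely cause, the event is possibly related and passes the causality filter. Protocol 7.4.1.1 also lists timing as a causality factor, which favours attribution soon after inhalation. Only events judged unlikely or unrelated fail. The exclusion of moderate events does not depend on attribution at all.
- **An AESI row of 0 v 0 is not a given.** The category interval pools both AESIs, so it would also need no qualifying palpitations in either arm. The pooling itself is a reason to show bronchospasm separately.
- **A filter has a use.** It keeps background events out of the count. If sites recognise drug-caused events well, it could sharpen the contrast. That supports keeping the narrow row, but not relying on it alone.
- **Safety is descriptive.** Protocol 8.6 plans no formal test, and Protocol section 1 reports no local tolerance signal in five earlier studies. This limits the weight of the point.

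**Conclusion.** The asymmetry is real on the text, and the gap is narrow. Bronchospasm that is not severe, or that the site judges unlikely to be related or unrelated, is left out of the AESI count and its interval. If fewer than 31 of 610 patients have the term, those events appear only as by-arm counts. At the assumed 15 v 3, the missing estimate would be 3.9 points (1.3 to 7.0).

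Every count and rate used here is assumed, as is the share of events that passes the filter. The threshold takes the safety population as the planned 610. The documents do not show that such an imbalance is likely, or that the causality scale would push bronchospasm towards unlikely. They show that the plan would print no interval for it. This is a cheap improvement to the reporting of safety. It is not a flaw in data capture or in any formal test.

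**What to change.** Keep the AESI definition and its row as they are. In the SAP 10.1 adverse event summary, add a separate row for treatment-emergent bronchospasm:

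- regardless of investigator attribution and regardless of frequency
- shown twice, for any severity and for moderate or worse
- with its own 95% Newcombe interval, not pooled with palpitations
- restricted to 4 hours after a dose only if AE onset times are recorded, and otherwise covering the treatment period.

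The last condition matters because SAP 7.3.3 handles AE start by day, month and year, and Protocol 7.7.2 does not mention an onset time. The case report form is not among the documents, so this needs checking.

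The change affects the analysis only: site reporting and patient management are untouched. Severity and arm are already available, so the cost is a sentence of SAP text and the added row. The downside is that some background COVID-19 events enter both arms' counts and widen the interval slightly.
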